12.1.3 Follow up of adverse events

An AE should be followed until it has resolved, has a stable sequelae, the investigator determines that it is no longer clinically significant, or the subject is lost to follow up. This follow-up requirement applies to AEs, SAEs, and AEs of special interest; further details regarding follow up of PDILI events is provided in Section 12.2.1.4.

If an AE is ongoing at the end of the study for a subject, follow up should be provided until resolution/stable level of sequelae is achieved, or until the investigator no longer deems that it is clinically significant, or until the subject is lost to follow up. If no follow up is provided, the investigator must provide a justification. The follow up will usually be continued for 8 weeks after the subject has discontinued his/her IMP.

Information on SAEs obtained after clinical database lock will be captured through the PS database without limitation of time.

12.1.4 Pregnancy

If an investigator is notified that a subject has become pregnant after the first intake of any IMP, the investigator must immediately notify UCB's PS department by providing the completed Pregnancy Report and Outcome form (for contact details see SAE reporting information at the beginning of this protocol). The subject should be withdrawn from the study as soon as pregnancy is known (by positive pregnancy test), and the following should be completed:

The subject should return for a PEOT Visit.

• The subject should immediately stop the intake of the IMP or be down-titrated as instructed at the PEOT Visit.

The investigator must inform the subject of information currently known about potential risks and about available treatment alternatives.

The pregnancy will be documented on the Pregnancy Report and Outcome form provided to the investigator. The progression of the pregnancy and the eventual birth (if applicable) must be followed up using the Pregnancy Report and Outcome form in which the investigator has to report on the health of the mother and of the child. Every reasonable attempt should be made to follow the health of the child for 30 days after birth for any significant medical issues. In certain circumstances, UCB may request that follow up is continued for a period longer than 30 days. If the subject is lost to follow up and/or refuses to give information, written documentation of attempts to contact the subject needs to be provided by the investigator and filed at the site. UCB's PS department is the primary contact for any questions related to the data collection for the pregnancy, eventual birth, and follow up.

In cases where the partner of a male subject enrolled in a clinical study becomes pregnant, the investigator or designee is asked to contact the subject to request consent of the partner via the Partner Pregnancy Consent form that has been approved by the responsible IRB/IEC and should be available in the investigator site file. In case of questions about the consent process, the investigator may contact the UCB/CRO contract monitor for the study. The investigator will complete the Pregnancy Report and Outcome form and send it to UCB's PS department (for contact details see SAE reporting information at the beginning of this protocol) only after the partner has agreed that additional information can be captured and has provided the signed Partner Pregnancy Consent form. UCB's PS department is also the primary contact for any questions related to the data collection for the partner pregnancy, eventual birth, and follow up.

A pregnancy becomes an SAE in the following circumstances: miscarriage, abortion (elective or spontaneous), unintended pregnancy after hormonal contraceptive failure (if the hormonal contraceptive was correctly used), ectopic pregnancy, fetal demise, or any congenital anomaly/birth defect of the baby. Those SAEs must be additionally reported using the Investigator SAE Report Form.

12.1.5 Suspected transmission of an infectious agent via a medicinal product

For the purposes of reporting, any suspected transmission of an infectious agent via a medicinal product should be considered as an SAE; such cases must be reported immediately, recorded in the AE module of the eCRF, and followed as any other SAE. Any organism, virus, or infectious particle (eg, prion protein transmitting transmissible spongiform encephalopathy), pathogenic or nonpathogenic, is considered an infectious agent.

12.1.7 Overdose of investigational medicinal product

notice and solution of the second sec

which the safety of UCB7665 will be assessed. The safety variables to be used and the decision rules will be specified in the DMC charter. Further details of these interim analyses are given in Section 14.7.

Thus, selected data from this study will be reviewed periodically to detect as early as possible any safety concern(s) related to the IMP so that investigators, clinical study subjects, regulatory authorities, and IRBs/IECs will be informed appropriately and as early as possible.

The sponsor study physician or medically qualified designee/equivalent will conduct an ongoing review of SAEs and perform ongoing SAE reconciliations in collaboration with the PS representative.

As appropriate for the stage of development and accumulated experience with the IMP, medically qualified personnel at UCB may identify additional safety measures (eg, AEs, vital signs, laboratory or ECG results) for which data will be periodically reviewed during the course of the study.

Hypersensitivity and adverse reactions 12.1.9

In the event of a severe infusion or anaphylactic reaction requiring corticosteroid and/or epinephrine therapy, the subject must permanently discontinue IMP and be managed as described in Section 18.8.

In case of occurrence of a hypersensitivity reaction (not determined by the investigator to be a minor local reaction at the infusion site, such as minimal itching) and depending upon its severity, appropriate countermeasures will immediately be taken by the investigator. The cytokine samples must be taken for infusion reactions.

If the investigator does not initially choose to discontinue the infusion of IMP and symptoms persist or escalate during continued infusion, the infusion should be stopped. In case of any severe infusion reaction(s), the infusion of IMP must be stopped immediately and appropriate treatment initiated, as necessary, at the discretion of the investigator and in accordance with the standard of care.

Moderate or severe anaphylactic reactions should be diagnosed using Sampson's Criteria (Sampson et al, 2006) as described in Section 18.9. In the event of an anaphylactic reaction the infusion must be discontinued immediately and appropriate emergency resuscitation measures implemented.

12.1.10 Management of severe headache

Severe headache is defined as severe pain limiting self-care activities of daily living (ADL) or new/prolonged hospitalization for management of headache or life-threatening consequences requiring urgent medical intervention. Self-care ADL refers to bathing, dressing and undressing, feeding self, using the toilet, and taking medications. Treatment of headache will be provided as clinically indicated according to the local guidelines. Subjects experiencing severe headache will complete the Headache Questionnaire and will complete the questionnaire daily until resolution (ie, if headache l normal collection of AEs should and and assessment (

Subjects experiencing severe headache will complete the Headache Questionnaire and will complete the questionnaire daily until resolution (ie, if headache becomes moderate or mild, normal collection of AEs should apply); this assessment will be followed by a neurological assessment (including fundoscopy). Further workup will be performed (if indicated) at the discretion of the investigator and may include, eg, a computed tomography scan, magnetic resonance imaging and/or a lumbar puncture for cerebral spinal fluid collection. In addition, assessment of exploratory safety biomarkers should be performed for subjects experiencing severe headache. These investigations will be performed in order to further understand the mechanism of headache in these subjects.

Details of neurological examination to be performed are provided in Section 12.3.6. The Headache Questionnaire is available in Section 18.10.

12.1.11 Management of moderate or severe diarrhea

Moderate or severe diarrhea is defined as an increase of \geq 4 stools per day over Baseline or incontinence due to urgency of diarrhea or new/prolonged hospitalization for management of diarrhea or limiting self-care ADL or life-threatening consequences requiring urgent medical intervention.

Stool collection and analysis will be performed for subjects reporting moderate or severe diarrhea. The frequency of stool sampling will be as clinically indicated in the opinion of the investigator. Analysis of stool samples will be performed locally. In addition, collection of blood samples for assessment of exploratory safety biomarkers is required for subjects with moderate to severe GI disturbances including diarrhea.

Treatment of diarrhea will be provided as clinically indicated according to the local guidelines.

or variations thereof May include but not limited to the following biomarkers listed below. Samples collected for exploratory safety biomarkers at Baseline (Visit 2) and 4 hours post dosing (Visit 2) for all subjects and during follow up only in subjects with severe headache and/or moderate to severe GI disturbances. The Baseline samples will only be analysed in case the subject experienced a severe headache and/or moderate to severe GI disturbance.

12.2.1 **Evaluation of PDILI**

The PDILI IMP discontinuation criteria for this study are provided in Section 6.4.1, with the accompanying required follow-up investigation and monitoring detailed below. All PDILI events must be reported as an AE and reported to the study site and sponsor within 24 hours of learning of their occurrence. Any PDILI event that meets the criterion for potential Hy's Law must be reported as an AE of special interest (see Section 12.1.1.3), and, if applicable, also reported as an SAE (see Section 12.1.1.2).

Evaluation of PDILI consists of the diagnostic testing and continued monitoring included in Table 12.3 (specific tests dependent on laboratory results and corresponding symptoms) and consultation with a local hepatologist (if applicable; discussed in Section 12.2.1.1). The local hepatologist is the expert usually consulted by the treating physician for assessment and management of potential hepatic disease. This would usually be a hepatologist, but may be a gastroenterologist. Additional investigation and monitoring may be required and adapted based on the diagnosis after the cause of the liver injury/abnormality is confirmed (details in Section 12.2.1.4).

The results of all monitoring, including laboratory testing and other testing, should be made available to the study site and sponsor. $\mathbb{A}^{\mathbb{Q}}$

All initial tests resulting in abnormal hepatic laboratory values need to be repeated, but appropriate medical action must not be delayed waiting for the repeat result.

If tests are done locally for more rapid results, a concurrent sample should also be sent to the central laboratory whenever possible. Medical care decisions are to be made initially using the most rapidly available results and a conservative approach must be taken if the results from the 2 laboratory tests are significantly different. Data from the local and central laboratory are to be recorded on the applicable eCRF pages.

When IMP is discontinued, all concomitant medications and herbal supplements that are not medically necessary should also be discontinued. In these cases, the investigator should also consider dose reduction for medically necessary concomitant medication and consider changing any medically required concomitant medication known to be hepatotoxic to a suitable alternative.

When IMP is stopped due to PDILI (as described in Section 6.4.1), IMP must be permanently discontinued unless a subsequent alternative diagnosis fully explains the hepatic findings. If a subsequent alternative diagnosis fully explains the hepatic findings, and the requirements provided in Section 12.2.1.2.1 are met, rechallenge with IMP may be appropriate.

REPACTOR CONTRACTOR OF THE CONTRACTOR OF THE OF THE

Laboratory	value		Immediate		Follow up	12/10
ALT or AST	Total bilirubin	Symptoms ^a of hepatitis or hypersensitivity	Consultation requirements	Actions	Testing	Evaluation
≥3xULN	≥2xULN ^b	NA	Hepatology consult. ^c Medical monitor must be notified within 24 hours	Immediate, permanent IMP discontinuation.	Essential: Must have repeat liver chemistry values and additional testing completed	Monitoring of liver chemistry values at least twice per week until values normalize, stabilize or return to within Baseline values. ^d
≥3xULN	NA	Yes	(eg, by laboratory alert) and subject discussed with medical monitor ASAP.	Immediate, temporary or permanent, IMP discontinuation.	ASAP (see Section 12.2.1.3); recommended to occur at the site with HCP.	values.
≥3xULN (and ≥2x Baseline) and <5xULN	<2xULN	No	Discussion with medical monitor required if the criterion that allows for IMP continuation is met.	Further investigation – immediate IMP discontinuation not required (see Section 12.2.1.2).	Not required unless otherwise medically indicated (at discretion of investigator).	
≥5xULN (and ≥2x Baseline)	<2xULN	No	Discussion with medical monitor required Hepatology consult required if ALT or AST ≥8xULN	Immediate, permanent IMP discontinuation.	Essential: Every attempt must be made to have repeat liver chemistry values and additional testing completed within 48 hours at the site with HCP (see Section 12.2.1.3).	Monitoring of liver chemistry values at least twice per week until values normalize, stabilize or return to within Baseline values. ^d
Confidential	this docume	St. Co	Pa	ge 79 of 193		

. a : 4: -4: £.

. sep 201, MG0002

Table 12.3: Required investigations and follow up for PDILI

Laboratory	value		Immediate		Follow up	Vario
ALT or AST	Total bilirubin	Symptoms ^a of hepatitis or hypersensitivity	Consultation requirements	Actions	Testing	Evaluation

ALP=alkaline phosphatase; ALT=alanine aminotransferase; ASAP=as soon as possible; AST=aspartate aminotransferase; HCP=healthcare practitioner; IMP=investigational medicinal product; NA=not applicable; PDILI=potential drug-induced liver injury; ULN=upper limit of normal

^a Hepatitis symptoms include fatigue, nausea, vomiting, and right upper quadrant pain or tenderness; hypersensitivity symptoms include eosinophilia (>5%), rash, and fever (without clear alternative cause).

^b If the subject also has $\geq 2xULN$ ALP, the possibility of an indication of biliary obstruction should be discussed with the medical monitor.

^c Details provided in Section 12.2.1.1. The local hepatologist is the expert usually consulted by the treating physician for assessment and management of potential hepatic disease. This would usually be a hepatologist, but may be a gastroenterologist.

stoenter.
Joe stroenter.
Joe responsible physician
FEDACCIED Unitation
FEDACUMENT
FEDACUMENT ^d Unless an alternative monitoring schedule is agreed by the investigator and UCB responsible physician. Determination of stabilization is at the discretion of the investigator in consultation with the hepatologist (as applicable) and UCB responsible physician as needed.

Confidential

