Subjects MAY be withdrawn from the study at the discretion of investigator, medical monitor, and study physician if any of the following events occur:

Subject is noncompliant with the study procedures or medications in the opinion of the investigator.

Subjects who withdraw from the study or discontinue IMP should complete the assessments outlined for the Premature End Of Treatment (PEOT) Visit (see Table 5.1 and Section 8.5). Subjects will be encouraged to return to the clinic/hospital to complete the Observation Period Visits and the FV (approximately 8 weeks after the final study drug administration).

Investigators should attempt to obtain information on subjects in the case of withdrawal.

variations thereof For subjects considered as lost to follow up, the investigator should make an effort (at least 1 phone call and 1 written message to the subject), and document his/her effort (date and 5 summary of the phone call and copy of the written message in the source documents), to s complete the final evaluation. All results of these evaluations and observations, together with a narrative description of the reason(s) for IMP discontinuation and subject withdrawal, must be recorded in the source documents. The eCRF must document the primary reason for withdrawal or discontinuation, plus whether or not the blind was broken, with the reason and date for this.

Investigators should contact the medical monitor, whenever possible, to discuss the withdrawal of a subject in advance. Subjects who are withdrawn will not be replaced.

Potential drug-induced liver injury IMP discontinuation criteria 6.4.1

Subjects with potential drug-induced liver injury (PDILI) must be assessed to determine if IMP must be discontinued. In addition, all concomitant medications and herbal supplements that are not medically necessary should also be discontinued.

The PDILI criteria below require *immediate and permanent* discontinuation of study drug:

- Subjects with either of the following:
 - ALT or AST \geq 5xULN
 - ALT or AST \geq 3xULN and coexisting total bilirubin \geq 2xULN

The PDILI criterion below requires immediate discontinuation of study drug:

Subjects with ALT or AST ≥3xULN who exhibit temporally associated symptoms of hepatitis or hypersensitivity. Hepatitis symptoms include fatigue, nausea, vomiting, right upper quadrant pain or tenderness. Hypersensitivity symptoms include fever (without clear alternative cause), rash, or eosinophilia (ie, >5%).

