If a nondrug-related cause for the symptoms can be confirmed, these subjects may resume study drug administration after discussion with the responsible UCB physician, but only when the requirements for rechallenge with study drug as provided in Section 12.2.1.2.1 are followed.

The PDIM criterion below allows for subjects to continue on study drug at the discretion of the investigator.

• Subjects with ALT or AST \geq 3xULN (and \geq 2x Baseline) and <5xULN, total

bilirubin <2xULN, and no eosinophilia (ie, $\le5\%$), with no fever, rash, or symptoms of hepatitis (eg. fatigue, nausea, vomiting, right upper quadrant pain or tenderness).

Evaluation of PDILI must be initiated as described in Section 12.2.1. If subjects are unable to comply with the applicable monitoring schedule, IMP must be discontinued immediately.

iv

Investigators should attempt to obtain information on subjects in the case of IMP discontinuation to complete the final evaluation. Subjects with PDILI should not be withdrawn from the study until investigation and monitoring are complete. All results of these evaluations and variations thereof observations, as well as the reason(s) for IMP discontinuation and subject withdrawal (if applicable), must be recorded in the source documents. The eCRF must document the primary reason for IMP discontinuation.

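### For one liver-injury combination Table 12.3 permits a temporary stop where Section 6.4.1 requires a permanent one, and the Baseline and rechallenge wording is also not aligned

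*Protocol*

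**What the plan says.** **Protocol Section 6.4.1** has three stop criteria and one that lets dosing continue.

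- Under the wording "The PDILI criteria below require *immediate and permanent* discontinuation of study drug" it lists two criteria: ALT or AST ≥5xULN, and ALT or AST ≥3xULN with bilirubin ≥2xULN. The first carries no condition on symptoms, bilirubin or Baseline.
- A third criterion requires an immediate stop, not described as permanent, at ≥3xULN for subjects "who exhibit temporally associated symptoms of hepatitis or hypersensitivity". It has no upper enzyme limit. Only here does 6.4.1 offer a way back: if a cause other than the drug is confirmed, "these subjects may resume study drug administration after discussion with the responsible UCB physician", subject to Section 12.2.1.2.1.

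**Protocol Section 12.2.1** opens with "The PDILI IMP discontinuation criteria for this study are provided in Section 6.4.1". It later says, of stops made under 6.4.1, "IMP must be permanently discontinued unless a subsequent alternative diagnosis fully explains the hepatic findings". Rechallenge may then be considered if 12.2.1.2.1 is met.

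**Table 12.3** has four rows, numbered here in order:

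1. ≥3xULN, bilirubin ≥2xULN, any symptom status: permanent stop.
2. ≥3xULN, any bilirubin, symptoms present: "Immediate, temporary or permanent, IMP discontinuation".
3. ≥3xULN (and at least twice Baseline) and <5xULN, bilirubin <2xULN, no symptoms: a stop is not required.
4. ≥5xULN (and at least twice Baseline), bilirubin <2xULN, no symptoms: permanent stop.

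The testing requirement for rows 1 and 2 begins "Essential: Must have repeat liver chemistry values and additional testing completed", as soon as possible. Row 4 says "Every attempt must be made to have repeat liver chemistry values and additional testing completed within 48 hours".

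**Section 12.2.1.2** sends sites to both 6.4.1 and Table 12.3 for the action and gives no order of priority. **Section 12.2.1.2.1** opens restart to subjects stopped under some of the criteria, without naming which.

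**The concern.** A liver stopping rule should give the same answer wherever the site looks. Here the table's only ≥5xULN row is confined to subjects without symptoms. A symptomatic subject at the same enzyme and bilirubin values drops to row 2, where a temporary stop is an option. The looser action goes to the subject with more evidence of liver injury.

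The combination is not far-fetched in this population. The protocol counts fatigue as a hepatitis symptom, and the trial measures fatigue in myasthenia gravis with a 55-item instrument (Section 9.3.2). Section 6.4.1 asks for a temporal association between symptoms and enzyme rise; Table 12.3 and its footnote do not repeat that.

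Two smaller mismatches go with it. Row 4 has a Baseline condition that 6.4.1 does not have. And the sections do not state in the same terms which stops can lead to rechallenge. At stake is subject safety and clear site instructions. Nothing here bears on the Visit 9 endpoint, the sample size or the primary analysis.

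**Working it through.** The plan gives no figure to reproduce, so the check sets the two texts side by side.

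**Stop action.** Inputs are the Section 6.4.1 criteria and the Table 12.3 rows. Two enzyme bands × two bilirubin bands × symptoms no or yes gives 2 × 2 × 2 = 8 combinations. One rule is used within each text: if several criteria or rows match, the stricter applies. The table below takes the twice-Baseline conditions as met.

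| ALT/AST (xULN) | Bilirubin (xULN) | Symptoms | Section 6.4.1 | Table 12.3 | Result |
|---|---|---|---|---|---|
| 3 to <5 | <2 | No | may continue | row 3: may continue | agree |
| 3 to <5 | <2 | Yes | stop, may resume | row 2: temporary allowed | agree |
| 3 to <5 | ≥2 | No | permanent | row 1: permanent | agree |
| 3 to <5 | ≥2 | Yes | permanent | rows 1 and 2; row 1 permanent | agree |
| ≥5 | <2 | No | permanent | row 4: permanent | agree |
| ≥5 | <2 | Yes | permanent | row 2 only: temporary allowed | **differ** |
| ≥5 | ≥2 | No | permanent | row 1: permanent | agree |
| ≥5 | ≥2 | Yes | permanent | rows 1 and 2; row 1 permanent | agree |

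Seven combinations agree and one differs.

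**Baseline condition in row 4.** A value v ≥5xULN fails the condition when v < 2 × Baseline, that is, when Baseline > v/2, which is at least 5/2 = 2.5xULN. Exclusion criterion 15 bars ALT or AST >2xULN. At a Baseline of 2xULN, 5xULN is 5/2 = 2.5 times Baseline, so the condition is met. But SAP Section 3.3 defines Baseline for chemistry as the predose Day 1 value, with the Screening value only as a fallback. For a raised value under the exclusion limit at Screening, criterion 15 asks for a repeat before dosing only where possible, and sends a clinically relevant increase to discussion with the medical monitor. A Day 1 Baseline above 2.5xULN is therefore unlikely but not ruled out. In that case an asymptomatic subject at ≥5xULN but below twice Baseline, with bilirubin <2xULN, would meet the permanent criterion in 6.4.1 and match no table row, making a second combination that differs.

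Row 3 has the same condition, but so does the matching continuation criterion in 6.4.1, so those two agree.

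**Rechallenge.** Section 6.4.1 offers resumption under one of its three stop criteria, the symptomatic one. The general sentence in 12.2.1 refers to stops under 6.4.1 without distinction, so on its face it reaches all three. Section 12.2.1.2.1 narrows this to an unnamed subset. The wording is therefore open for the two criteria that 6.4.1 calls permanent.

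**The case against.** The strongest reply is that the stopping rule has one home. Section 6.4, item 7 of the mandatory discontinuation list, cites 6.4.1 alone; 12.2.1 says the criteria are there; and the title of Table 12.3 concerns investigations and follow-up. Row 2 permits a temporary stop but does not require one, so a site that stops permanently at ≥5xULN complies with both texts. The same reasoning settles the overlap inside 6.4.1, where a symptomatic subject at ≥5xULN meets two criteria: meeting a permanent criterion means a permanent stop. This largely stands and is why the point is minor. It does not remove the mismatch, because 12.2.1.2, the section on the immediate action, cites the table alongside 6.4.1 with no priority.

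On rechallenge, a reader might infer that 12.2.1 positively grants it after every stop. The documents do not support that. The sentence makes it conditional on 12.2.1.2.1, whose unnamed subset can be read as the one criterion that 6.4.1 allows. The defect is ambiguity, not proven contradiction.

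A reader might also infer that symptomatic subjects with marked elevations would be put back on drug. Restart needs every condition in 12.2.1.2.1, including a confirmed alternative diagnosis, ALT/AST not above 3xULN, bilirubin <1.5xULN, and approval by the sponsor's physician, the DMC and a hepatologist. It also needs an absence of other treatment options, which would be hard to show when inclusion criterion 4 enrols candidates for IVIg or plasma exchange and Section 7.8.3 names both as rescue. Timing adds a further barrier: Table 5.1, footnote d, allows at most 9 days from the previous dose, so the main realistic opening is the planned interval from Day 15 to Day 29.

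**Conclusion.** The point holds in a narrow form. Table 12.3 falls short of the controlling criteria in 6.4.1 in one of eight combinations: ≥5xULN, bilirubin <2xULN, symptoms present. A second mismatch is possible through row 4's Baseline condition, but only if Baseline exceeds 2.5xULN. Separately, 12.2.1 and 12.2.1.2.1 leave it unclear whether a stop that 6.4.1 calls permanent can be considered for rechallenge.

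The count assumes that the stricter matching rule governs within each text. The documents give no rate for such cases; with 42 subjects planned and entry limited to enzymes at or below 2xULN, few are expected. Severity is minor: an inconsistency worth correcting in a safety rule, not a gap that leaves subjects unprotected.

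**What to change.** 1. Cap the symptomatic row of Table 12.3, and the symptomatic criterion in 6.4.1, at ≥3xULN to <5xULN with bilirubin <2xULN. Higher values are already covered by the permanent criteria.
2. Add a table row for ≥5xULN, bilirubin <2xULN, symptoms present: immediate permanent discontinuation, with the consultation and testing requirements of rows 1 and 2. Widening row 4 instead would weaken the testing instruction for these subjects.
3. Delete the twice-Baseline condition from the ≥5xULN row so that it matches 6.4.1.
4. Amend 12.2.1 and 12.2.1.2.1 to limit rechallenge to the capped symptomatic criterion, in line with 6.4.1.

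After these changes all eight combinations give the same action in both places and each falls in exactly one row. The remaining Baseline condition, in row 3, is shared by 6.4.1.

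The cost is a few lines of protocol text, with no new visits, subjects or types of procedure. The one substantive loss is that a rare subject stopped under a permanent criterion, whose findings are later fully explained by another cause, could not be rechallenged.
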